10.13. Unscheduled Possible Recurrence Visit

If CDI recurrence is suspected any time within 8 weeks of the last study enema due to new onset documentation of three or more unformed/loose (i.e., Bristol Stool Scale type 6-7) stools within 24 or fewer consecutive hours for at least two consecutive days, possible treatment failure should be assessed. An in-office visit should occur if a recurrence of CDI is suspected. The subject must provide a fresh stool sample for shipment to the central laboratory to test for the presence of *C. difficile*.

The following study activities/data will be collected at the Unscheduled Possible Recurrence visit:

- Collect fresh stool sample to send to the central laboratory for analysis
- Assess recurrence of CDI
 - Start date of symptoms, current symptoms, central laboratory testing result, source of episode (*CDI recurrence, healthcare contagion, community contagion, or unknown*), treatment(s)
- Vital signs: temperature, pulse, blood pressure, respiration
- Adverse event collection, including the new onsets of obesity, metabolic syndrome, pre-diabetes, diabetes and/or autoimmune disorders
- Changes to concomitant medications since last visit
- Cdiff32 health-related quality of life questionnaire
- For subjects who consented to the Optional Stool Sample collection, remind the subject to collect and ship a stool sample to Rebiotix.

Treatment failure (CDI recurrence) is defined as:

- The presence of CDI diarrhea within 8 weeks of administration of a study enema, which includes a positive stool test for *C. difficile* as determined by the central laboratory.

To ensure consistency across clinical sites for the determination of study failure, the central laboratory will perform the required C. DIFF QUIK CHEK COMPLETE® Test (QCC Test) rapid enzyme immunoassay test for glutamate dehydrogenase (GDH) and toxins A and B.

In the case of suspected treatment failure where there is an immediate concern for subject safety, including the potential for serious adverse events, a test may be conducted at the site or other laboratory known to the site **in addition to** sending a sample to the central laboratory for testing. In the event the test results from the central laboratory differ from that of a local laboratory, the results from the central laboratory will be used in determination of treatment failure and eligibility to receive a second treatment with RBX2660, instead of the other laboratory's result.

10.14. Second RBX2660 Treatment

Subjects with a documented treatment failure meeting the protocol definition (**Section 7.3.6**) after receipt of the first RBX2660 enema may be scheduled for administration of a second RBX2660 enema. If antibiotics are given to control symptoms, a 24-72 hour washout period prior to administration of a second RBX2660 enema is required, however the second enema must be administered within 21 calendar days of failure determination.

In order to receive the second treatment with RBX2660, a subject must have documentation of the following:

- Meeting all treatment failure criteria as defined by the protocol (**Section 7.3.6**)
- Compliance to the washout period (discontinuation of antibiotics for 24-72 hours prior to administration visit) is confirmed, if applicable
- Negative urine-dipstick pregnancy test for subject of childbearing potential to confirm that they are not pregnant on the date of administration
- Enema administration is to occur within 21 calendar days of failure determination

The following study activities/data will be collected at this visit prior to IP administration:

- Onsite urine pregnancy test for subjects of child bearing potential
- Assess vital signs: temperature, pulse, blood pressure, respiration
- Changes to concomitant medications since the last visit
- Assess recurrence of CDI
- Assess for adverse events since enrollment
- Date and time of the last bowel movement prior to the enema
- Did the subject void his/her bladder prior to entering the administration room

Following successful completion of the above listed items, IP is administered via enema per the Instructions for Use and standard site procedure; see **Section 9.8.3**.

The following information is collected specific to the administration of the IP:

- Enema clinical batch number
- Enema administration start and end time
- Enema administration status (successful; attempted, not completed; opened, not administered)
- Subject position for enema
 - Length of time subject was in position after enema
- Did the Rebiotix kit components perform as expected
- Note whether the subject expelled or leaked any of the IP during the observation period
 - How long was the enema retained before the expulsion or leakage (minutes)
 - What was the estimated amount of enema that was expelled or leaked

Subjects remain at the site under supervision for at least one hour post-IP administration for vital sign assessment (temperature, heart rate, blood pressure, respiratory rate) about every 15 minutes and observation. If the subject's vital signs do not return to the Baseline visit's (**Section 10.8**) pre-administration values $\pm 20\%$, assess the subject for a possible AE.

All safety data collected are to be recorded and reported as required in **Section 11**.

If a subject receives a second RBX2660 enema, follow-up is completed via telephone assessment at 1-week, 4-weeks, 8-weeks, and 6 months per **Section 10.14.1** after the second RBX2660 treatment.

No additional treatments of RBX2660 beyond a second enema will be administered as part of this study for treatment failures.

The study will be considered complete when all subjects have reached their 6-month follow-up after the last study enema received, including second enemas, or have exited, whichever is earlier.

10.14.1. 1-week, 4-weeks, 8-weeks, 6-month Telephone Assessment

- Subject's weight, self-reported
- Adverse event collection, including new onsets of obesity, metabolic syndrome, pre-diabetes, diabetes and/or autoimmune disorders
- Changes to concomitant medications since the last visit
- For subjects who consented to the Optional Stool Sample collection, remind the subject to collect and ship a stool sample to Rebiotix

10.15. Study Exit

A Study Exit eCRF will be completed for each subject who is treated. Data to be collected at this visit includes exit date and reason for study exit. This visit may occur in conjunction with the 6-month Follow-Up visit for subjects who complete the study and do not have ongoing adverse events that have not stabilized.

The following information will be collected on the Study Exit eCRF:

- Exit date
- Reason for study exit
 - Completed Study
 - Screen Failure
 - Withdrawal by subject
 - Study Terminated by Sponsor
 - Investigator withdrawal
 - Adverse Event
 - Death
 - Lost to Follow-Up
 - Other (to be specified)

Additional data will be collected when the following occur:

- Medication changes
- Adverse Events

10.16. Subject Withdrawal or Termination

A subject's study participation is considered complete once the 6-month telephone assessment is conducted after receiving the last study enema or the subject exits the study, whichever comes first. A subject may withdraw at any time for any reason or be withdrawn from the study prematurely for the following reasons:

- Withdrawal of consent by subject
- Lost to follow-up
- Failure to comply to study requirements
- Termination of study by the sponsor
- Death
- Other (to be specified)

The reason for withdrawal is recorded on the Study Exit eCRF. In the event that a subject requests to withdraw from the study, every attempt should be made to have the subject provide an update on the current status of any adverse events and current medications. If the subject has an ongoing adverse event deemed related to IP or enema procedure, recommend following the subject until the adverse event has resolved or stabilized prior to exiting the study.

For a subject who is suspected of being lost-to-follow-up, a minimum of three attempts must be made to contact subjects using two different contact methods (e.g., telephone, email, text, and letter); one attempt must be a registered postal letter or traceable courier notice (e.g., FedEx Express) to the subject's last known address. The contact attempts and methods are to be recorded on the Study Exit eCRF. The date to use for the subject as lost to follow-up is the date of last actual encounter with the subject, such as the last phone call contact or visit.

Completion of a Study Exit eCRF is required for all treated subjects when they exit the study regardless of reason, including completion of all study requirements, visits and assessments. Subjects who were determined to be screen failures or otherwise exited prior to receiving a dose of the study drug will also have a Study Exit eCRF completed.

11. Assessment of Safety

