7.3.3.3. Prohibited Medications

Prohibited medications include any oral vancomycin, metronidazole, fidaxomicin, rifaximin, nitazoxanide, bezlotoxumab, or IVIG through the 8-week follow-up assessment unless newly prescribed by a treating investigator during the course of the study as a result of recurrent CDI diagnosis. Use of IVIG for treatment of a non-CDI indication is allowed. Use of non-dietary probiotics from Screening through 8 weeks after receiving the last study enema (including OTC and prescription) is also prohibited. Medication information will be collected at the Screening visit and changes in medications will be recorded throughout the study.

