11.1. Adverse Event Management

Adverse events (AE), which include clinical laboratory test variables, will be monitored and documented from the time of informed consent. Subjects should be instructed to report any AE that they experience to the investigator. Investigators should make an assessment for AEs at each visit and record the event on the appropriate eCRF.

Wherever possible, a specific disease or syndrome rather than individual associated signs and symptoms should be identified by the investigator and recorded on the eCRF. However, if an observed or reported sign or symptom is not considered a component of a specific disease or syndrome by the investigator, it should be recorded as a separate adverse event on the eCRF. Additionally, the condition that led to a medical or surgical procedure (e.g., surgery, endoscopy, tooth extraction, or transfusion) should be recorded as an AE, not the procedure.

Any medical condition already present at Screening should not be reported as an AE unless the medical condition or signs or symptoms present at Screening change in severity or seriousness at any time during the study. In this case, it should be reported as an AE.

Clinically significant abnormal laboratory or other examination (e.g., electrocardiogram) findings that are detected during the study or are present at Screening and significantly worsen during the study should be assessed for an AE. The investigator will exercise their medical and scientific judgment in deciding whether an abnormal laboratory finding or other abnormal assessment is clinically significant. Clinically significant abnormal laboratory values occurring during the clinical study will be followed until repeat tests return to normal, stabilize, or are no longer clinically significant. Any abnormal test that is determined to be an error does not require reporting as an AE.

For all CDI recurrences, information is recorded on the Follow-up eCRF and applicable CDI eCRF. Recurrence of CDI is not to be reported as an AE unless hospitalization \geq 24 hours is required as part of treatment. If hospitalization \geq 24 hours is required, the event qualifies as an AE and is to be reported as an SAE (see **Section 11.14** for sponsor reporting requirements).

AEs should be followed until the event resolves or the subject exits the study. Chronic condition is defined as a condition lasting > 3 months.

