5.3 Analysis Populations

5.3.1 *Safety Population*

The safety population (SP) is defined as the population of subjects who had any treatment attempted or completed. The safety population will be used in analysis of all safety endpoints including the primary endpoint.

5.3.2 *Intent-to-Treat Population*

The ITT population is defined as all subjects enrolled, excluding screen failures.

5.3.3 *Modified Intent-to-Treat Population*

Analysis of the efficacy endpoints will use the modified Intent-to-Treat (mITT) population as a primary efficacy analysis population. The mITT population is defined as all subjects who successfully received treatment but excluding:

- subjects in whom treatment was attempted but not completed and;
- subjects who discontinue from the study prior to evaluation of treatment failure/success for the 8-week efficacy endpoint if the reason for exit is not related to CDI symptoms. Reason for exit will be

captured on the exit form to allow for identification of such subjects. Examples of reasons unrelated to CDI symptoms may include:

- Withdrawal of consent
- Death unrelated to CDI

5.3.4 *Per-Protocol Population*

The per-protocol (PP) population will consist of all subjects who successfully received treatment analyzed according to the treatment they received, excluding:

- Subjects who have documented protocol deviations to inclusion or exclusion criteria.
- Subjects who exited prior to the 8-week efficacy evaluation if the reason for exit was not related to CDI symptoms in the same manner as the mITT population.

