6.6 Safety Analysis

The SP will be used to summarize all adverse event data, unless otherwise specified. Safety data will be summarized for events after the first and second enemas, as well as combined. Events occurring after the first enema will be counted up to the date of retreatment, or study exit. Events on, or after, the date of a second enema will be assigned to the second period. The combined analysis will consider all events, after first enema through study exit, even if a subject receives a second enema.

6.6.1 *Analyses Supporting the Primary Safety Endpoint*

Assessment of the primary safety objective will include descriptive statistics and be performed on the SP. Additional sub-analyses of safety data may be performed on sub-populations.

6.6.2 *Other Safety Analyses*

6.6.2.1 *Adverse Events*

A summary of adverse events, TEAEs, non-serious TEAEs, and serious TEAEs will be summarized using counts of the number of events and frequencies (counts and percentages) of

the number of subjects. The incidence of each preferred term (PT) within the primary system organ class (SOC) as well as overall primary SOC incidence will be presented. Summaries may also be presented by PT, irrespective of SOC. A subject with multiple events coded to the same PT within a primary SOC will be counted only once for the PT within the primary SOC. Likewise, a subject with multiple events coded to the same SOC will be counted only once within the SOC.

An overall summary of AEs will present the incidence of (1) all TEAEs, (2) TEAEs related to IP, (3) TEAEs related to enema procedure, (4) TEAEs related to *C. difficile* disease, (5) TEAEs related to a preexisting condition, (6) serious TEAEs, (7) serious TEAEs related to IP, (8) serious TEAEs related to the enema procedure, (9) serious TEAEs related to *C. difficile* disease, (10) serious TEAEs related to a preexisting condition, and (11) TEAEs leading to death.

Frequency of occurrence and number and percent of subjects experiencing an event through 6 months follow-up will be presented for both the first and second enemas as follows:

- All TEAEs
- TEAEs by maximum severity
- TEAEs by relatedness to IP
- TEAEs by relatedness to *C. difficile* disease
- TEAEs by relatedness to enema procedure
- TEAEs by relatedness to preexisting condition
- TEAEs resulting in subject withdrawal
- TEAEs resulting in death
- Serious TEAEs
- Serious TEAEs by maximum severity
- Serious TEAEs by relatedness to IP

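### Protocol 10.16 lets a dosed subject be withdrawn from the study for non-compliance without separating the end of treatment from the end of observation

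*Protocol*

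**What the plan says.** - **Withdrawal rule (Protocol 10.16).** "A subject may withdraw at any time for any reason or be withdrawn from the study prematurely for the following reasons"; one listed reason is "Failure to comply to study requirements". There is no limit to the period before dosing. The section treats participation as complete at exit. For a related AE still open, it says to "recommend following the subject until the adverse event has resolved or stabilized prior to exiting the study".
- **End of AE follow-up (Protocol 11.1).** "AEs should be followed until the event resolves or the subject exits the study".
- **End of AE counting (SAP 6.6).** "Events occurring after the first enema will be counted up to the date of retreatment, or study exit". The combined first-plus-second-enema analysis also runs to study exit.
- **What survives exit.** Protocol 11.6.1 keeps SAEs reportable until 6 months after the last enema, and 11.6.2 requires each SAE to be followed to an end point. Protocol 11.8 requires AEs related to product or enema to be followed until they resolve or stabilise.
- **Populations (SAP 5.3 and 6.7.1.2).** mITT and PP drop subjects who leave before the 8-week evaluation "if the reason for exit is not related to CDI symptoms" (the mITT wording; PP follows it). The Safety Population keeps anyone in whom treatment was attempted. The ITT sensitivity analysis counts every exit before week 8 as a failure.
- **Exit form (Protocol 10.15).** The reasons listed include investigator withdrawal and an open category for other reasons, but not non-compliance.

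**The concern.** The primary objective is safety and tolerability, with follow-up to 6 months. Exposure cannot be undone once an enema has been given, so ending observation because a subject complies poorly gains no information and loses some. The rule does not distinguish a subject who should receive no further study treatment from one who should no longer be observed.

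Three things are at stake. First, the primary endpoint is a count of subjects with at least one related TEAE, so unobserved time can only lower it. Second, a new chronic condition must last more than 3 months to qualify, so an early exit can prevent its confirmation. Third, non-compliance may be related to outcome. Protocol 7.3.3.3 states: "Prohibited medications include any oral vancomycin, metronidazole, fidaxomicin, rifaximin, nitazoxanide, bezlotoxumab, or IVIG through the 8-week follow-up assessment". The same sentence exempts drugs newly prescribed by a treating investigator for an on-study recurrent CDI diagnosis. Use outside that exemption is non-compliance and could plausibly be prompted by returning symptoms. If the exit is then classed as unrelated to CDI symptoms, a likely failure leaves the main efficacy population.

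**Working it through.** The plan gives no dropout rate, no expected number of non-compliance withdrawals and no power calculation (SAP 3.3), so there is no figure of its own to reproduce. The check is a reading of the rules in sequence, followed by illustrations on assumed rates.

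**1. What happens to a dosed subject withdrawn for non-compliance**
- Scheduled contacts end (10.16), and non-serious AEs are followed only to exit (11.1).
- A later SAE is reportable (11.6.1), but only once the site knows of it, and no scheduled contact remains to reveal it. If it is reported, SAP 6.6 still stops counting at exit.
- The effort in 10.16 to obtain a last AE update is tied to a subject's own request to withdraw. The three-attempt contact rule is tied to suspected loss to follow-up. Neither is stated for a site-initiated withdrawal.
- SAP 7.3 imputes nothing for the unobserved period.
- The mITT rule relies on the exit form to identify the reason. Without a non-compliance category, the exit would have to be recorded under another heading, and the mITT decision becomes hard to audit.

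**2. Observation lost.** On the SAP's day numbering (enema day 1, month 6 day 181), an exit on day 8 loses (181 − 8)/180 = 96% of follow-up. An exit on day 57 loses (181 − 57)/180 = 69%.

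**3. Primary endpoint, extreme bounds.** Inputs: N = 750 (the cap); 17.2% related TEAEs among those retained, borrowed from retrospective Protocol 2019-02 (product-related only); k = number withdrawn, from an assumed share w; r = 17.2% of (750 − k), rounded. The lower bound r/750 has no withdrawn subject with a related TEAE. The upper bound (r + k)/750 has one in every withdrawn subject.

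| w (assumed) | k | r | Lower | Upper |
|---|---|---|---|---|
| 1% | 8 | 128 | 17.1% | 18.1% |
| 2% | 15 | 126 | 16.8% | 18.8% |
| 5% | 38 | 122 | 16.3% | 21.3% |
| 10% | 75 | 116 | 15.5% | 25.5% |

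**4. mITT success.** Let s be true success overall, s_w success among those withdrawn, and w the share withdrawn. Assume all exits fall before the 8-week evaluation and are classed as unrelated to CDI symptoms, with no other exits. Then mITT = (s − w·s_w)/(1 − w), and ITT with exits as failures = s − w·s_w. Take s = 75% and s_w = 50%. Both are assumed; for context, the protocol reports 70.4% and 78.9% in two earlier studies.
- w = 2%: mITT = (0.75 − 0.02 × 0.50)/0.98 = 75.5%, which is 0.5 points high. ITT = 0.75 − 0.01 = 74.0%, which is 1.0 point low.
- w = 5%: mITT = (0.75 − 0.05 × 0.50)/0.95 = 76.3%, which is 1.3 points high. ITT = 0.75 − 0.025 = 72.5%, which is 2.5 points low.

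The mITT bias equals w(s − s_w)/(1 − w), so it vanishes if withdrawn subjects succeed as often as the rest.

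**The case against.** The strongest reply is that the documents already contain most of the protection.

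- **Withdrawal is permitted, not required.** Protocol 10.1 makes missed or late contacts reportable as deviations, and Protocol 7.5 keeps failures who are not re-treated on their original schedule. This stands, but nothing stops a site from using the withdrawal ground after dosing.
- **Safety follow-up does not end entirely.** A reader might infer that all AE, SAE and CDI collection stops. The documents do not support that: SAEs stay reportable to 6 months and known related AEs must be followed. What is lost is scheduled detection of new non-serious events. Many events also come early: in Protocol 2013-001, 66.5% of AEs occurred by the 7-day visit, so the upper bounds above are extreme.
- **Loss from mITT is conditional.** A reader might infer that every such withdrawal leaves mITT. It does so only before the 8-week evaluation and only if classed as unrelated to CDI symptoms. A symptom-linked exit can stay in, and a subject already evaluated as a failure is not removed. Non-compliance is not among the SAP's examples of unrelated reasons, so its classification is open.
- **A conservative check exists.** The ITT analysis would show a shift of failures out of mITT. It does not recover the observations.
- **Exposure is not always over after one visit.** A documented failure may receive a second enema. Eligibility for that enema is a separate matter from whether observation continues.
- **The efficacy effect is small.** At N = 750 and 75%, the 95% half-width is 1.96 × √(0.75 × 0.25/750) = 3.1 points, more than the 0.5-1.3 points above, and the endpoint is a descriptive secondary one. This is a fair reason to treat the point as modest.

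**Conclusion.** The point holds in a limited form. Protocol 10.16 allows observation of a dosed subject to end for non-compliance, and Protocol 11.1 and SAP 6.6 carry that into truncated AE follow-up and counting. The main loss is undetected new non-serious related TEAEs and unconfirmed chronic conditions. The second is a conditional loss from mITT and PP.

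The size is unknown because the documents give no withdrawal rate. Under the assumed 2-5%, with 50% against 75% success and all exits before week 8, mITT success is overstated by 0.5-1.3 points. At 1-2% both effects are small. A reader might go further and conclude that the efficacy estimate is biased or that safety follow-up collapses. The documents show only that the rules permit avoidable missing data, not that it will occur on any particular scale. The change is still worth making because it is cheap and protects the study's primary purpose.

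**What to change.** In Protocol 10.16, state that after dosing, non-compliance is recorded as a protocol deviation and may not by itself end observation. The subject stays in scheduled AE and CDI follow-up through month 6 after the last enema unless consent is withdrawn or the subject is lost to follow-up. Apply this also when the reason would be entered as investigator withdrawal or other; restricting the one listed reason would leave those routes open for the same exit. The change concerns observation only and leaves eligibility for a second enema as it is.

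Align the exit-form reasons in 10.15 with 10.16 so that any remaining non-compliance exit is identifiable, and state in SAP 5.3.3 and 5.3.4 how it is classed. Reconcile 10.16 (follow-up of open related AEs recommended), 11.1 (follow-up to exit), 11.6 (SAEs to 6 months) and 11.8 (follow-up of related AEs required).

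Cost: short protocol text and exit-form guidance, plus some contacts with poorly compliant subjects. With five scheduled contacts after the first enema, 15-38 subjects would mean at most 15 × 5 = 75 to 38 × 5 = 190 contacts, and not all would succeed. The cap of 750 does not change.
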